### **Treatment emergent adverse events (TEAEs)**

TEAEs are defined as those, which start between the start of the first infusion of blinatumomab and 30 days after the end of the last infusion during the **treatment period**. In case the start time or the exact start date of the AE is not available and it is thus unclear, whether an AE started after start of first blinatumomab infusion or before 30 days after the end of last infusion then the AE will be included in the analysis as TEAE.

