### **Primary Endpoint:**

Incidence of treatment-emergent and treatment-related adverse events

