### 6.2.2.2 DLT Observation Period

The time for the DLT assessment will be the first 14 days of treatment based on the observation that most adverse events are usually observed within a few days of treatment initiation and dose step. If the dose modification per Table 5 is followed, time for the DLT assessment will be the first 21 days. An observed DLT will be attributed to the blinatumomab dose level administered at the time at which the DLT occurred.

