# 9.2 Safety Event Reporting Procedures

# 9.2.1 Adverse Events

# 9.2.1.1 Reporting Procedures for Adverse Events That do not Meet Serious Criteria

The investigator is responsible for ensuring that all adverse events observed by the investigator or reported by the subject that occur after enrollment through 30 days after the last dose of study treatment or the safety follow-up visit (whichever is longer) are reported using the applicable eCRF (eg, Adverse Event Summary).

The investigator must assign the following adverse event attributes:

- Adverse event diagnosis or syndrome(s), if known (if not known, signs or symptoms)
- Dates of onset and resolution (if resolved)
- Severity (and/or toxicity per protocol)

Date: 20 March 2019 Page 85 of 122

- Assessment of relatedness to blinatumomab or medical device
- Action taken

Product: Blinatumomab

If the severity of an adverse event changes from the date of onset to the date of resolution, record as a single event with the worst severity on the Adverse Event Summary eCRF.

The adverse event grading scale used will be the CTCAE. The grading scale used in this study is described in Appendix A. The investigator must assess whether the adverse event is possibly related to blinatumomab. This relationship is indicated by a "yes" or "no" response to the question: Is there a reasonable possibility that the event may have been caused by blinatumomab or other protocol-specified therapies?

The investigator must assess whether the adverse event is possibly related to any study-mandated activity (eg, administration of investigational product, protocol-required therapies, device(s) and/or procedure (including any screening procedure(s)). This relationship is indicated by a "yes" or "no" response to the question: "Is there a reasonable possibility that the event may have been caused by a study activity (eg, administration of investigational product, protocol-required therapies, device(s)), and/or procedure"?

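### The SAP classes an adverse event as treatment-emergent by its start date alone, so an event recorded before dosing that worsens on blinatumomab is left out of the treatment-emergent tables

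*SAP*

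**What the plan says.** **Definition.** SAP section 6 sets the rule by onset: "TEAEs are defined as those, which start between the start of the first infusion of blinatumomab and 30 days after". The window closes 30 days after the final infusion stops. The only extension is for an event whose start date or time is unclear; "then the AE will be included in the analysis as TEAE".

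**Collection.** Protocol 9.2.1.1 asks sites to report adverse events "that occur after enrollment through 30 days after the last dose of study treatment" or the safety follow-up visit, whichever is longer. For serious events, 9.2.2 starts the clock at informed consent. Both starting points precede the first infusion.

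**Recording.** If severity changes during an event, the site must "record as a single event with the worst severity on the Adverse Event Summary eCRF". Protocol 9.1.1 repeats the instruction. The attributes listed in 9.2.1.1 include dates of onset and resolution, but no date for a change of grade.

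**Use.** The expansion cohort's primary endpoint is "Incidence of treatment-emergent and treatment-related adverse events". Protocol 10.4.4 tabulates it in the same way as the treatment-emergent tables. SAP 10.7.1 lists treatment-emergent, grade 3 and above, serious, treatment-related and fatal events side by side. It does not say whether the later categories are restricted to treatment-emergent events.

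**The concern.** Each rule is ordinary by itself. Together they leave a gap. An event can begin at low grade after enrolment, be on the eCRF before the infusion starts, and then become severe on drug. The single record shows the severe grade and the early onset, so the SAP treats the whole event as not treatment-emergent. The part that matters for safety, the worsening on treatment, is lost with it.

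The expansion cohort tests no hypothesis; its purpose is to describe adverse events on blinatumomab. A rule that omits documented on-drug worsening from the treatment-emergent tables works against that purpose. It is also at odds with the SAP's own caution: an event with an unclear start is counted, while one known to have worsened on drug is not.

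**Working it through.** The documents state no figure on this point, so there is none to reproduce. The check is to run the possible cases through the rules.

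| Case | What is recorded | Treatment-emergent under SAP 6? |
|---|---|---|
| Event starts after the first infusion | One record, on-treatment onset | Yes |
| Start date or time unclear | One record | Yes, by the SAP's extension |
| Non-serious condition present before enrolment, worsens on drug beyond expectation | Worsening is itself an adverse event (protocol 9.1.1), with on-treatment onset | Yes |
| Laboratory change not clinically significant before dosing, significant on drug | Generally no record before dosing (protocol 9.2.1.1); the event starts on drug | Yes |
| Adverse event starts between enrolment and first infusion, worsens on drug | One record, worst grade, pre-dose onset | **No, at any grade** |
| Serious event starts between consent and first infusion, worsens on drug | One record, worst grade, pre-dose onset | **No, at any grade** |

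The gap is the last two rows. The pre-existing-condition clause does not close it, because an event already recorded falls under the single-record instruction in the same section.

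**Size per subject.** Inputs: about 65 expansion subjects (protocol 10.2) and 21 Phase 2 subjects. With k subjects lost from a term, its incidence falls by k/N.

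- Expansion: 1/65 = 1.5 points; 2/65 = 3.1; 5/65 = 7.7.
- Phase 2: 1/21 = 4.8 points.
- SAP 10.7.1 allows an optional table of terms reaching 5% of subjects. One lost subject takes a term from 4/65 = 6.2% to 3/65 = 4.6%, below that cut.

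Adults and children are summarised separately, so with 65 enrolled the share per subject within either group exceeds 1.5 points. The documents do not give the split.

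**How often.** The documents give neither the gap between enrolment and first infusion nor the frequency of such events. As an assumption only, let q be the proportion of subjects with at least one. The expected number affected is 65q, and the chance of at least one is 1 − (1 − q)^65, taking subjects as independent.

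| Assumed q | Expected subjects | Chance of at least one |
|---|---|---|
| 1% | 0.65 | 0.48 |
| 5% | 3.25 | 0.96 |
| 10% | 6.5 | >0.99 |
| 20% | 13 | about 1.00 |

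These are subjects with any such event, spread over all terms; they are not losses for one term.

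**The case against.** The strongest reply is that the gap is narrow, and much of that reply stands.

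- **The window is short.** One might suppose it takes in the dexamethasone pre-phase and the screening lumbar puncture. Protocol 3.1 and 7.2.1 place both within screening, which runs until enrolment. Non-serious problems arising then are pre-existing conditions, and their worsening on drug is a new, treatment-emergent event.
- **Laboratory examples are weak.** Clinically insignificant findings are generally not adverse events. SAP 10.7.2 also provides shift tables from baseline to worst value for selected laboratory parameters, with baseline normally taken before infusion on day 1. Those tables do not replace adverse event incidence, and they do not cover fever, infection or neurologic events.
- **Overall incidence should hardly change.** All subjects in the cited pediatric study had adverse events (protocol 2.1.2), so nearly everyone is likely to have some treatment-emergent event.
- **Some tables may keep the event.** SAP 10.7.1 does not limit the treatment-related, grade 3 and above, serious or fatal tables to treatment-emergent events. A reader might infer that the event leaves the expansion primary endpoint altogether. Only its exclusion from the treatment-emergent part is established.
- **Not every rule leans downward.** Unclear starts count as treatment-emergent and the worst grade is kept, so a net understatement of all safety results is not shown.

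A reader might also infer that a dose-limiting toxicity could be assigned to the wrong dose level when an event straddles the day 8 dose step. The documents do not support this. Protocol 6.2.2.2 says: "An observed DLT will be attributed to the blinatumomab dose level administered at the time at which the DLT occurred". Under the grade 3 criterion a grade 1 or 2 event is not yet such a toxicity, and no section substitutes adverse event onset. Section 6.2.2.3 also gives the expansion doses as those of the starting cohorts.

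**Conclusion.** The concern holds as a gap in the treatment-emergent definition. An adverse event first arising between enrolment and first infusion, or a serious event between consent and first infusion, that worsens on blinatumomab is excluded from the treatment-emergent tables by the plan as written. This follows from the text and needs no outside assumption.

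The consequence is confined to preferred-term and severity tables. It is 1.5 points per lost subject and term at 65 subjects, and the number lost cannot be derived from the documents. It is tempting to apply a percentage loss to the grade 3 rates quoted from the earlier pediatric study. No document says what share of such events begins before dosing, so no such estimate is justified. The point deserves a correction because it concerns the rule behind a primary endpoint; nothing here suggests that the overall safety conclusion would change.

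**What to change.** 1. **SAP section 6.** Define a treatment-emergent event as one that starts, or increases in CTCAE grade, from the first infusion until 30 days after the last infusion ends.
2. **Protocol 9.1.1 and 9.2.1.1, and the eCRF guidelines.** When an event recorded before dosing worsens after the first infusion, capture the date of the grade increase or open a new line.
3. **SAP 10.7.1.** State whether the grade 3 and above, serious, fatal and treatment-related tables are subsets of treatment-emergent events.
4. **Records already entered.** As a sensitivity analysis, repeat the tables with events added that began before dosing, were ongoing at first infusion and have worst grade 3 or higher. Existing onset and resolution dates are enough to identify them. Note that some may have peaked before dosing, so the added count is an upper limit for grade 3 and above. Worsening from grade 1 to 2 is not recovered.

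The cost is one SAP sentence, one clarification, and one eCRF date field or guideline line. Adverse event rates become slightly higher. The SAP change log refers to a study report for the primary analysis, so small differences from that report should be expected and explained.

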## **7. Analysis Subsets**

### **7.1 Full Analysis Set**

All subjects who received any infusion of blinatumomab are included in the full analysis set (FAS) for phase 1b and phase 2 portion of the study respectively. This definition is in line with the intent-to-treat (ITT) principle in single-arm open-label studies. The efficacy analysis will be based on subjects from the FAS.

### **7.2 Safety Analysis Set**

For each part of the study, the safety analysis set will be the same as the FAS for that part.

### **7.3 DLT Analysis Set**

For the assessment of DLTs, only DLT evaluable subjects will be included.

### **7.4 Per Protocol Set(s) (PPS)**

For each part of the study, the per protocol set will include all subjects from the FAS for that part who do not have any major relevant protocol violations which could have an impact on the efficacy evaluations.

### 7.5 Pooled Adult Analysis Set (PAS)

The pooled analysis set will be an exploratory pooled analysis set that will include adult subjects from the FAS from Phase 1b and from the FAS from Phase 2. This additional pooled analysis will be performed for safety data and the primary and secondary efficacy endpoints for adult subjects.

### 7.6 Pharmacokinetic/Pharmacodynamic Analyses Set(s)

All subjects who received any infusion of blinatumomab and had at least one PK sample collected will be included in the PK analysis set. These subjects will be evaluated for PK unless significant protocol deviations affect the data analysis or if key dosing, dosing interruption or sampling information is missing. All subjects who had cytokine and/or lymphocyte subset samples collected at any time during the study will be included in the PD analysis set.

### 7.7 Expansion Analysis Set (EAS)

**All subjects who are enrolled in the expansion cohort and received any infusion of blinatumomab will be included in the Expansion analysis set.**

## 8. Interim Analysis and Early Stopping Guidelines

An interim analysis will be performed at the latest during the Phase 2 part of the study after the first 13 adult subjects who are enrolled in the first stage have either discontinued treatment or completed their first 2 treatment cycles. The purpose of this interim analysis will **be to** determine whether the second stage of the Phase 2 part of the protocol should continue per the study design. The study will be stopped at the first stage if 1 or fewer out of 13 subjects are observed with any CR/CRh\* in the first stage of the Phase 2 part of the study. Should 2 or more subjects achieve a CR/CRh\* prior to first 13 subjects evaluated, the first stage criteria would be met. An interim analysis may be performed based on Phase 1b data only for early JNDA filing if needed.

Additional interim analyses may be performed to provide data for regulatory interactions. The purpose of these interim data analyses is to provide the safety and efficacy information updates.

For Phase 1b dose-cohort study de-escalation and stopping rules, please refer to protocol section 6.2.2. During phase 1b, DRC will review safety data from each cohort in the Phase 1b part to select a dose for the Phase 2 part. In addition, DSMB will also oversee safety approximately every 6 months.

---

## **9. Data Screening and Acceptance**

### **9.1 General Principles**

The database will be subjected to edit checks outlined in the data validation specifications plan by Amgen Clinical Data Management (CDM) department. Any outstanding data issues will be communicated to CDM for resolution before the database is locked.

Quintiles Inc. will provide support for data management activities and assess the quantity, quality and statistical characteristics of the data relative to the requirements of the planned analyses.

### **9.2 Data Handling and Electronic Transfer of Data**

Amgen's CDM department will provide all data to be used in the planned analyses. This study will use the RAVE database.

The results of the central lab, such as cytomorphology (% of blasts in bone marrow), HAMA, and lymphocytes will be analyzed by central laboratory vendors. Antibody, Cytokine, and PK samples will be shipped from sites to the Biolanalytics department at Amgen for analysis. These additional laboratory data will be transferred to CDM and then loaded into the clinical database.

All data for this study will be submitted directly to CDM for inclusion into the clinical study database.

Once all data queries have been resolved, and source verified and initial locked, the database will be final locked. The final analysis will be conducted on the final lock data. The final SAS data sets will be archived.

### **9.3 Handling of Missing and Incomplete Data**

In general, missing data will be treated as missing, unless otherwise specified. For primary efficacy endpoint, patients with missing response will be considered as non-responders. Attempts will be made to characterize the missing data. Instead, it is recommended to perform a set of sensitivity analyses to demonstrate how missing values may influence estimates and the corresponding test decisions.

Data will be analyzed as retrieved from the database provided by CDM except for analyses requiring imputations. The imputed data will be written to the derived datasets but not to the raw data. The imputation algorithm will be described in the Data Definition Table (DDT). Please refer to [Appendix D](#) for the general imputation algorithm.

#### **9.4 Detection of Bias**

The sources of possible bias will be summarized and be considered while interpreting study results. Sources of bias to be considered may include protocol violations or informative censoring.

#### **9.5 Outliers**

No statistical test for outliers will be performed. Any suspected outliers will be investigated by the study team and will be included in the database unless determined to be an error or there is supporting evidence or explanation to justify the exclusion. Any outliers excluded from the analysis will be discussed in the CSR, including the reasons for exclusion and the impact of their exclusion on the study.

#### **9.6 Distributional Characteristics**

Due to the single-arm study, the summaries of analyses results are descriptive in nature.

#### **9.7 Validation of Statistical Analyses**

SAS® version 9.2 or higher will be utilized in programming for all statistical analyses, derived data and tables, listings and figures (TFL) creation. Where possible, the standard departmental macros will be used. Testing and validation plans for all programs will be developed in accordance with departmental guidelines or Metronomia procedures.

### **10. Statistical Methods of Analysis**

#### **10.1 General Principles**

Adult subjects and pediatric subjects will be summarized separately. Pediatric subjects will not enroll into phase 2 for hypothesis testing. The efficacy endpoint results of pediatric subjects will be listed and descriptive.

#### **Analysis for expansion cohort will be based on Expansion analysis set.**

A clinical study report will be generated for the primary analysis. The long-term follow-up period of the study will be updated in the report once all the subjects have completed long-term follow-up, until lost to follow-up, or until death (whichever occurs first). All documented parameters will be adequately evaluated. The data will be summarized overall, and by assigned dose cohort using suitable descriptive measures.

The DLT findings during the Phase 1b part will be tabulated. Descriptive statistics for demographic and baseline characteristics will be summarized.

For categorical variables, the number and percentage of subjects in each category will be summarized. Continuous variables will be summarized by n, mean, standard deviation, median, Q1 (25th percentile), Q3 (75th percentile), minimum, and maximum values.

Point estimates for efficacy endpoints incidences will be accompanied by 2-sided 95% exact binomial confidence intervals (CIs) (Clopper and Pearson, 1934). For time to event variables, the Kaplan-Meier (K-M) method (Kaplan and Meier, 1958) will be used to estimate the quartiles (median, 25th and 75th percentiles) of the variable, along with 95% two-sided CI (Brookmeyer and Crowley, 1982) or others specified. The range, first quartile, and the third quartile of the observation time will be provided in addition. K-M estimates will be presented graphically.

No adjustments for multiplicity are planned for the analyses of the efficacy endpoints. Additional exploratory analyses will be performed to adjust for the baseline covariates as deemed appropriate.

## **10.2 Subject Accountability**

The number of subjects who screened, enrolled, received at least one dose of blinatumomab, completed the first two cycles and follow-up period, completed study, prematurely withdrew, and the reason for premature withdrawal will be tabulated and summarized overall and by dose cohort.

## **10.3 Important Protocol Deviations**

Important protocol deviations will be listed. Decisions on the exclusion of a patient from the PPS are on a by-patient basis. All criteria and reasons for these decisions will be documented. Eligibility deviations are defined in the protocol.

## **10.4 Demographic and Baseline Characteristics**

Demographics and other baseline characteristics will be summarized overall by dose cohort by means of summary statistics (number of patients, number of patients with missing data, mean, standard deviations, minimum, median, maximum) for continuous variables and by frequencies for categorical variables.

Demographic data and other baseline characteristics will be summarized **using FAS for Phase 1b and Phase 2 part of the study whereas Expansion Analysis Set will be used for Expansion cohort.** For the following variables, frequency tables will be produced:

- Gender
- Race
- Age by group
- Disease evaluation (B-ALL subtype) and genetic abnormality
- Study entry criteria (Primary refractory, refractory to salvage therapy, first relapse with remission duration less than 12 months, untreated 2nd or greater relapse, and relapse after allo-HSCT)
- Any extramedullary disease
- Prior HSCT status
- Number of relapses
- Refractory
  - Number of patients primary refractory
  - Number of patients relapse refractory (refractory to salvage therapy)
- Number of prior salvage therapy
- ECOG (adults) or Lansky/Karnofsky (pediatric) performance status

The following continuous variables will be summarized:

- Age
- Time since last HSCT [months]
- Time since initial diagnosis [months]
- Time between initial diagnosis and first relapse [months]
- Time between latest relapse and first dose of blinatumomab [months]
- Time between last HSCT and latest relapse [months]

#### **10.5 DLT**

Incidence rate of DLT will be summarized for adult subjects and pediatric subjects separately for Phase 1b Part of the study. The DLT summary will be based on the DLT analysis set.

#### **10.6 Efficacy Analyses**

The efficacy analyses for phase 1b and phase 2 parts of the study were summarized in tables below.

**Table 3. Efficacy Endpoint Summary for Phase 1b**

| Phase 1b Endpoint   | Primary Summary and Analysis Method   | Sensitivity Analysis   |
|---|---|--|
| Primary Efficacy Endpoint   |   |  |
| Response: CR/CRh* for adult subjects or M1 remission for pediatric subjects | 
 
Summary statistics of CR/CRh* rate for adult subjects or M1 remission rate for pediatric subjects within the first 2 cycles.
 
Sub-categories will also be provided. The rate will be estimated along with its 95% exact CI. FAS subjects without response data will be treated as non-responders.
 
 | 
 
Repeat the analysis for subjects in the FAS who had non-missing post-baseline response data.
 
May repeat the analysis for PPS when deemed appropriate.
 
 |
| Secondary Efficacy Endpoints  |   |  |
| Duration of Response (or TTHR)  | 
 
FAS subjects in first 2 cycles who achieved response (CR/CRh* for adult subjects or M1 remission for pediatric subjects) are included.
 
Cumulative incidence function considering competing risk will be provided when sample size is appropriate.
 
  | 
 
Censoring at the time of HSCT may be considered as deemed as appropriate.
 
  |
| Overall survival  | 
 
FAS subjects in first cycle will be used
 
K-M estimates will be utilized and 3, 6 and 12 months rates will be provided when sample size is enough.
 
  | 
 
Censoring at the time of HSCT may be considered as deem as appropriate.
 
  |
| RFS   | 
 
FAS subjects in first 2 cycles who achieved response (CR/CRh* for adult subjects or M1 remission for pediatric subjects) are included.
 
K-M estimates will be utilized and 3, 6 and 12 months rates will be provided when sample size is appropriate.
 
   | 
 
Censoring at the time of HSCT may be considered as deem as appropriate.
 
  |
| Exploratory Efficacy Endpoints  |   |  |
| MRD response  | 
 
Summary statistics of MRD response in FAS. The rate will be estimated along with its 95% exact CI. Response rate is based on the number of subjects with a CR/CRh* and evaluable MRD.
 
   |  |
| Complete MRD response   | 
 
Summary statistics of Complete MRD response in FAS. The rate will be estimated along with its 95% exact CI. Response rate is based on the number of subjects with a CR/CRh* and evaluable MRD.
 
  |  |

